**INSTRUCTIONS**

This template is intended to help investigators prepare a protocol that includes all of the necessary information needed by the IRB to determine whether a study meets approval criteria. **Read the following instructions before proceeding:**

1. Use this protocol template for a PI initiated study that includes direct interactions with research subjects. Additional templates for other types of research protocols are available in the system Library.
2. If a section or question does not apply to your research study, type “Not Applicable” underneath.
3. Once completed, upload your protocol in the “Basic Information” screen in IRES IRB system.

## SECTION I: RESEARCH PLAN

1. **Statement of Purpose:** State the scientific aim(s) of the study, or the hypotheses to be tested.

The proposed project will use wearable technology to test the feasibility and efficacy of delivering a novel real-time smoking intervention to improve standard tobacco treatment. 50 adult daily smokers will be recruited from an outpatient tobacco treatment center to participate in an 8-week pilot intervention. Participants will be randomly assigned to a control group (standard treatment ST, n=25) or experimental group (standard treatment plus real-time smoking intervention ST+, n=25). The control group (ST) will not receive real-time feedback about their smoking. The experimental group (ST+) will receive real-time feedback as soon as smoking is detected using wearable technology during the 8-week intervention. Specific aims include:

**Aim 1: Evaluate the feasibility, acceptability, and helpfulness of the real-time smoking intervention.** We will characterize rates of adherence (i.e., number of days wearing the smartband) and evaluate participant satisfaction and perceived usefulness of the intervention using post-treatment interviews and ratings.

**Aim 2: Assess the preliminary efficacy of the real-time intervention as an adjunct to standard tobacco treatment.** We will compare biochemically confirmed 7-day point prevalence abstinence at the end of treatment (week 8) to estimate effect sizes for ST+ vs. ST. Additional outcomes will compare total number of days abstinent and changes in cigarettes per smoking day from baseline to end of treatment between ST+ and ST as proximal indices of good clinical response that are related to long-term cessation outcomes.

2. **Probable Duration of Project:** State the expected duration of the project, including all follow-up and data analysis activities.

2 years. We anticipate recruiting and enrolling 50 subjects over 20 months and will complete data entry and analysis by the end of 2 years.

3. **Background:** Describe the background information that led to the plan for this project. Provide references to support the expectation of obtaining useful scientific data.

[figure not shown]
Cigarette smoking is the leading cause of preventable death. The majority of current smokers want to quit, but most smoking quit attempts are unsuccessful, suggesting treatment innovations are needed. Mobile smoking treatments are gaining popularity and have many benefits, including that treatments are highly accessible, scalable, and can be provided in the user's natural environment. However, existing mobile interventions require users to manually record smoking behavior and decide if and when to access support, limiting the accuracy of information and the timeliness of the intervention. Recent innovations in wearable technology (e.g., smartbands) now allow for passive, automatic identification of smoking behavior through geospatial sensors and adaptive learning algorithms. Preliminary research indicates smoking can be identified reliably in real time using smartband technology, yet no studies have tested

whether intervening in the moment when smoking is detected can promote cessation during a quit attempt.

Real-time notifications as soon as smoking is detected may improve the timeliness of intervention delivery and enhance quitting success. According to cognitive theories of drug use, smoking behavior becomes highly automatic over time, such that smoking occurs quickly, efficiently, and without deliberate intention or awareness. Real-time notifications when smoking is detected may help promote cessation by bringing awareness to the smoking event, thereby reducing the automaticity of smoking and providing an opportunity to practice alternative coping strategies. Even after a lapse, or initial return to smoking after quitting, this real-time feedback may help individuals recover abstinence and protect against a return to smoking.

4. **Research Plan:** Summarize the study design and research procedures using non-technical language that can be readily understood by someone outside the discipline. **Be sure to distinguish between standard of care vs. research procedures when applicable, and include any flowcharts of visits specifying their individual times and lengths.** Describe the setting in which the research will take place.

**Overview:** The proposed study will evaluate the feasibility and efficacy of a real-time smoking intervention as an adjunct to enhance standard tobacco treatment. 50 adult smokers will be randomly assigned to a control group (standard tobacco treatment, ST, n=25) vs. an experimental group (standard treatment plus a real-time smoking intervention, ST+, n=25). Randomization to group (1:1) will be stratified by average number of cigarettes smoked per day at baseline (< or ≥ 10 cigarettes per day) to balance groups on smoking intensity. Enrolled participants will complete research visits at 4 weeks and 8 weeks (see Figure 1). Participants will receive financial compensation for their time spent completing research activities: \$20 for each appointment (week 0,4,8) for a total of \$60. Participants will earn a \$20 bonus for attending the last visit (week 8) and returning the smartband and charger. These visits will take place remotely in which the participant will speak with our research staff by phone or video call, at the tobacco clinic, at our research office, or at a location that is convenient, such as a public place.

**Recruitment:** We will recruit from the Yale Tobacco Treatment Service (TTS) and the Winchester chest clinic. These programs are a specialized outpatient services at Yale-New Haven Hospital that provides individual tobacco treatment to a large patient

population of current smokers. New patients referred to the TTS and Winchester chest clinic will be informed about the study and will be invited to set up a screening appointment if interested. To facilitate participant enrollment and retention, study procedures may take place in person or remotely (e.g., phone, secure video conference) when possible.

Screening Assessments: To screen for eligibility, participants will complete the following assessments including: 1) Smoking history to assess smoking quantity and frequency such as number of cigarettes per day and number of years smoked, 2) self-reported other tobacco and drug use for the past 30 days. Participants may also complete biochemical verification of smoking status, such as breath carbon monoxide (CO) measured in parts per million or cotinine measured in a small sample of urine or saliva.

Participants: Eligibility criteria include: (a) age 18 or older, (b) daily cigarette smoker, (c) seeking smoking cessation treatment at Yale TTS or Winchester chest clinic, (d) able to read and write in English, (d) owning a smartphone (smartphone ownership is estimated to be over 80% among adult smokers who are motivated to quit). Exclusion criteria include: (a) unstable psychiatric/medical conditions (e.g., suicidal ideation, acute psychosis, dementia), (b) current use of other tobacco products assessed via self-report, (c) current daily use of combustible marijuana. We exclude participants who use other tobacco products or smoke marijuana because the smartband system is only validated to detect and respond to cigarette smoking. We exclude participants who are regular users of combustible marijuana because this can elevate expired breath carbon monoxide (CO) making CO an inaccurate measure to confirm cigarette smoking status.

Experimental Methods: Eligible participants will be randomized to one of two treatment conditions (ST vs. ST+). All participants will receive standard outpatient tobacco treatment (ST) at the Yale Tobacco Treatment Service (TTS) or Winchester chest clinic following clinical practice guidelines. All patients receive up to 8 sessions of one-on-one counseling which focuses on setting a quit date within the first 2 weeks of treatment and discusses coping strategies and relapse prevention. Patients are encouraged to try smoking cessation pharmacotherapy and can obtain these medications over the counter or by prescription from the TTS or Winchester chest clinic. The experimental group (ST+) will receive standard care plus an adjunct treatment which involves wearing a smartband for the 8-week study and receiving real-time notifications as soon as smoking is detected with the embedded geospatial movement sensors in the smartband. There are multiple commercially available smartbands/smartwatches that are compatible with the real- time smoking monitoring system; for example, the Asus Zenwatch 2 pairs with the user's smartphone via Bluetooth connection. When smoking is detected, an alert is sent to the user through the band (vibration) and their smartphone app (alert) with a message indicating that smoking was just detected. The user can indicate yes/no if this smoking detection was accurate. Real-time smoking data is recorded for the user to review in their smartphone app and is available for the research team to view on a password-protected secure online dashboard. Data include only the timing and number of smoking events, labeled by subject ID. This real-time notification may disrupt the automaticity of smoking behavior and help bring awareness to smoking and related cues in the moment, which may enhance the individual's ability to anticipate and respond adaptively to cues in the future. The control group will also receive the smartband to wear for the 8 week study to control for demands associated with remembering to wear the band and charge it.

Measures: Baseline measures will be used to characterize the sample. Repeated measures will be used to assess changes in smoking and related constructs during treatment.

Demographic Questionnaires (week 0): Age, gender, marital status, employment status, occupation.

Smoking History (week 0): Smoking characteristics will be assessed, including the number of years of cigarette use, length of prior quit attempts, and prior treatments used.

Quitting Motivation and Confidence (week 0): Readiness to quit smoking and confidence quitting smoking will be measured on an 11-point scale (0=not at all, 10=extremely) using the contemplation ladder.

Discounting task (week 0): A brief computerized discounting task will be administered (5 questions each) to assess choice preference for cigarettes and money. Participants choose between a hypothetical smaller sooner reward or larger later reward, which is a validated measure of decision-making that has been shown to relate to treatment outcomes.

Timeline Follow-Back Interview (TLFB) (week 0,4,8): A standardized, validated, and reliable interview will be used to obtain quantity and frequency estimates of tobacco use, alcohol, and other drugs for the 30-days prior to baseline and at each research visit.

Biochemical Verification of Smoking Status (week 0,4,8): Assessed when needed to confirm reported abstinence via either expired breath carbon monoxide (CO) levels, which have a half-life of 2 hours or cotinine measured in a small sample of urine or saliva.

Nicotine Dependence (week 0,8): Measured by the Fagerström Test for Nicotine Dependence and the 4-item NIH PROMIS® measure for daily smokers.

Craving (week 0,4,8): Measured by the Questionnaire of Smoking Urges-Brief (QSU-Brief).

Strength of Smoking Habit (week 0,4,8): Measured with a 6-item Self-Report Habit index adapted and validated for smoking behavior, e.g. “Smoking is something I do automatically” rated on a 5-point scale (1=strongly disagree, 5=strongly agree).

Perceived Control Over Smoking (week 0,4,8): Measured with 3 valid, reliable items rated on a 7-point scale that have demonstrated associations with smoking outcome, e.g., “How much control do you feel you have over not smoking?” (1=no control, 7=complete control).

Approach-Avoidance Task (AAT) (week 0, 4, 8): An objective behavioral task that measures the tendency to automatically approach smoking stimuli (e.g., cigarettes). Our research team has used an adapted version of the approach-avoidance task (AAT) to measure smoking approach and avoidance action tendencies. The task starts with 20 practice trials in which participants learn to push or pull the joystick in response to picture format (landscape or portrait). The practice phase is followed by 160 test trials in which pictures of cigarette stimuli (e.g., cigarettes, cigarette packages) and non-cigarette stimuli (e.g., pencil) come equally in

push- or pull-format (this takes 5 to 10 minutes). Picture format (landscape or portrait) to response assignment (push or pull) is counterbalanced, with half the participants pulling landscape pictures and half portrait pictures. The smoking approach bias represents the relative difference between pushing and pulling the joystick in response to the smoking stimuli, measured as mean reaction time. Evidence supports reliable approach tendencies related to substance use and indicates that meaningful changes in automatic approach tendencies related to substance use outcomes can be detected after one week.

End of Treatment Ratings (week 8): We will evaluate participant satisfaction and perceived usefulness of the treatment across both conditions with post-treatment interviews and ratings.

Analytical Plan:

Data Management and Statistical Analyses: The proposed study will follow HIPAA guidelines for data collection, management, and monitoring. Data analyses will use the intention-to-treat (ITT) principle, where missing data will be treated as smoking. Data analyses will be conducted under the supervision of [name] who is a biostatistician. Data on quantitative outcomes will be examined for conformity to the normal distribution and transformation or non-parametric methods will be used if necessary.

Aim 1: Evaluate the feasibility, acceptability, and helpfulness of the real-time smoking intervention. We will use descriptive statistics to summarize participant ratings of satisfaction and perceived usefulness of the intervention at the end of treatment, including characterizing adherence and feasibility of using the smartband device based on self-report and objective adherence (i.e., number of days wearing the smartband).

Aim 2: Assess the preliminary efficacy of the real-time intervention as an adjunct to standard tobacco treatment. We will compare biochemically confirmed 7-day point prevalence abstinence at the end of treatment (i.e., reported abstinence from cigarettes during the last week of the study that is confirmed with CO≤ 4ppm or cotinine measured in a small sample of urine or saliva) to estimate effect sizes for ST+ vs. ST. We will also compare continuous outcome measures between ST+ and ST that are proximal indices of good clinical response: number of days abstinent and changes in cigarettes per smoking day from baseline to week 8. We will use independent sample t-tests to compare total days abstinent between ST+ and ST and a 2x2 mixed ANOVA (time x condition) to compare changes in cigarettes per smoking day from baseline to week 8.

5. Genetic Testing    N/A

A. Describe

- i. the types of future research to be conducted using the materials, specifying if immortalization of cell lines, whole exome or genome sequencing, genome wide association studies, or animal studies are planned *Write here*
- ii. the plan for the collection of material or the conditions under which material will be received *Write here*
- iii. the types of information about the donor/individual contributors that will be entered into a database *Write here*

HIC# 2000024740

iv. the methods to uphold confidentiality *Write here*

- B.** What are the conditions or procedures for sharing of materials and/or distributing for future research projects? *Write here*
- C.** Is widespread sharing of materials planned? *Write here*
- D.** When and under what conditions will materials be stripped of all identifiers? *Write here*
- E.** Can donor-subjects withdraw their materials at any time, and/or withdraw the identifiers that connect them to their materials? *Write here*
  - i. How will requests to withdraw materials be handled (e.g., material no longer identified: that is, anonymized) or material destroyed)? *Write here*
- F.** Describe the provisions for protection of participant privacy *Write here*
- G.** Describe the methods for the security of storage and sharing of materials *Write here*

6. **Subject Population:** Provide a detailed description of the types of human subjects who will be recruited into this study.

*Write here*

We will recruit current adult (at least 18 years old) daily smokers who are seeking smoking cessation treatment at Yale TTS or Winchester chest clinic. See detailed inclusion and exclusion criteria below (section 8).

7. **Subject classification:** Check off all classifications of subjects that will be specifically recruited for enrollment in the research project. Will subjects who may require additional safeguards or other considerations be enrolled in the study? If so, identify the population of subjects requiring special safeguards and provide a justification for their involvement.

 Children	 Healthy	 Fetal material, placenta, or dead fetus
 Non-English Speaking	 Prisoners	 Economically disadvantaged persons
 Decisionally Impaired	 Employees	 Pregnant women and/or fetuses
 Yale Students	 Females of childbearing potential	

NOTE: Is this research proposal designed to enroll children who are wards of the state as potential subjects?

Yes  No

8. **Inclusion/Exclusion Criteria:** What are the criteria used to determine subject inclusion or exclusion?

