2. How will the research data be collected, recorded and stored? Research data will be collected using in-person interviews, survey assessments, objective measures of smoking behavior (via the smartband), and self-reports. All identifiable information (names and demographic information) will be stored in a locked file cabinet. All participants will be assigned a study participant ID made up of numbers and letters. Subsequently, participants will be identified in the Case Report Forms (CRFs) only by that number (e.g., CM24). A list of IDs and the corresponding names will be maintained by the Principal Investigator and stored in a locked research cabinet. All other research data (interviews, survey assessments, objective measures of smoking behavior, and self-reports) will not contain identifiable information and will be labeled only with the subjects' unique numerical indicator. The smoking data captured from the smartband includes the time and date of smoking episodes. These data are available for the research team on a password-protected secure online dashboard.
3. How will the digital data be stored?  CD  DVD  Flash Drive  Portable Hard Drive  Secured Server  
 Laptop Computer  Desktop Computer  Other  
Digital data with PHI will be stored on a secured server. Digital data without PHI may be stored and analyzed on a laptop or desktop computer.

What methods and procedures will be used to safeguard the confidentiality and security of the identifiable study data and the storage media indicated above during and after the subject's participation in the study? Several steps will be taken to safeguard the confidentiality of subjects and their data. Right to privacy for participation in this research will be protected through coding of data and proper storage of research records. All research data that is collected will be assigned a study participant number and that number will be the only link between participant names/identifying information and the digital databases. The names of participants will not be associated with these data and assessments will be maintained according to participant study number. A master list connecting participant study numbers to participant names will be kept in a locked file cabinet where it can only be accessed by senior level project staff. Any information published as a result of the study will be in aggregate and such that it will not permit identification of any participant.

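### Does the Aim 1 smartband adherence measure need a stated data source, day-worn rule and denominator before it can be reported?

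*Combined protocol and SAP*

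**What the plan says.** Days of smartband wear appear in three places in the combined protocol and SAP.

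- **Section I, item 1, Aim 1:** "We will characterize rates of adherence (i.e., number of days wearing the smartband").
- **Section I, item 4, Analytical Plan, Aim 1:** descriptive statistics will cover adherence and feasibility, from self-report and from "objective adherence (i.e., number of days wearing the smartband").
- **Section I, item 12, Aim 1:** the same wording as the Analytical Plan.

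The data from the band are described separately.

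- **Section I, item 4, Experimental Methods, and item 9, Smoking Intervention Components:** "Data include only the timing and number of smoking events, labeled by subject ID".
- **Section IV, item 2:** "Research data will be collected using in-person interviews, survey assessments, objective measures of smoking behavior (via the smartband), and self-reports", and later "The smoking data captured from the smartband includes the time and date of smoking episodes".

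On the device and the wear period, Experimental Methods leaves the model open ("There are multiple commercially available smartbands/smartwatches that are compatible"). It has the experimental arm wear the band for the 8-week study, and adds: "The control group will also receive the smartband to wear for the 8 week study".

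The Analytical Plan adopts intention to treat, "where missing data will be treated as smoking". No other missing-data rule is given.

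**The concern.** Feasibility is half the purpose of this pilot, and days of wear is the one adherence measure that the plan spells out. Three things needed to calculate it are not written down.

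1. **Source.** Each description of the band's output concerns smoking events. No wear, charge or synchronisation record is named, and the open choice of model means that one cannot be inferred from the hardware.
2. **Day worn.** No minimum wear or signal is given, and no self-report item on wear is listed.
3. **Denominator.** The aims promise rates but describe a count. The only missing-data rule concerns smoking, so it does not say how days after withdrawal are treated.

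Two consequences are possible. The same wear data could give quite different adherence percentages, depending on how leavers are handled. And if days worn were inferred from days with a detected smoking event, a participant who was quitting successfully would look non-adherent.

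**Working it through.** The documents give no adherence figure, target or threshold, so there is no stated number to reproduce. The check is a reading of the text, followed by arithmetic on the wear period.

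**Inputs.** Wear period: 8 weeks × 7 = 56 days, both arms (Experimental Methods). Sample: 50 (Statement of Purpose). Dropout and day of exit are not given, so they are assumed: 10%, 20% or 30% leaving at day 14, 28 or 42, with the band worn every day until exit.

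**1. Do the passages on source contradict each other?** The sentence limiting the data to the timing and number of smoking events directly follows one about the real-time smoking data shown in the app and on the dashboard. Its natural subject is that feed, not everything the device logs. The Section IV list is a summary: it also omits the joystick task, which is certainly collected. The Analytical Plan sets the objective measure beside self-report, which points to the device or its app. The log is therefore unnamed, but nothing says that it does not exist.

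**2. One leaver.** Worn on days 1 to 14, then withdrawn:
- count of days, as the plan defines the measure: 14;
- rate on days in study: 14/14 = 100%;
- rate on the planned period: 14/56 = 25%.

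The contrast appears only once the count is turned into a percentage.

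**3. Sample of 50, exit at day 14.** The mean rate on days in study is 100%. On 56 days:
- 5 leave: (45 × 100 + 5 × 25)/50 = 92.5%, gap 7.5 points;
- 10 leave: (40 × 100 + 10 × 25)/50 = 85.0%, gap 15.0 points;
- 15 leave: (35 × 100 + 15 × 25)/50 = 77.5%, gap 22.5 points.

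The mean count over all 50 carries the same information as the 56-day rate. With 10 leavers it is (40 × 56 + 10 × 14)/50 = 47.6 days, and 47.6/56 = 85.0%.

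**4. Sensitivity to day of exit.** Under full wear, gap = dropout × (1 − exit day/56).

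| Exit day | 1 − exit day/56 | 10% leave | 20% leave | 30% leave |
|---|---|---|---|---|
| 14 | 0.75 | 7.5 | 15.0 | 22.5 |
| 28 | 0.50 | 5.0 | 10.0 | 15.0 |
| 42 | 0.25 | 2.5 | 5.0 | 7.5 |

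The gap (in points) depends on the assumed exit day as much as on the choice of denominator.

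**5. Smoking-event days as a stand-in for wear.** With perfect detection, a participant who wears the band for all 56 days and is abstinent on 28 would score (56 − 28)/56 = 50%. That would be a poor measure, but no passage proposes it.

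**6. What depends on the figure.** Aim 1 uses descriptive statistics only. No test, success criterion or decision to proceed is attached to days of wear, and Aim 2 and the sample-size paragraph do not use it.

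**The case for a change.** The strongest case for a change is that a descriptive statistic still needs a definition, above all in a study whose first aim is feasibility. The word rates does appear in the Statement of Purpose. Days in study and 56 days are both compatible with the text, and the 8-week period is never tied to the measure. A wear log that is not kept while the study runs may be impossible to recover later, and a few added sentences would cost nothing.

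Part of this stands: the wear record and the day-worn rule are absent from the documents, and removed or redacted pages do not appear to explain that. The rest carries less weight.

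- Both analysis sections speak of a number of days and never of a rate. The single mention of rates is explained on the spot as that same count.
- Intention to treat is stated for the data analyses in general. It is not tied to adherence by name, but it points towards everyone randomised rather than days in study.
- The absence of a listed self-report wear item shows little, because no individual item of the week 8 interviews and ratings is listed. The self-report component also means that device days are not necessarily the only numerical adherence measure.
- A team committed to reporting objective days of wear has to keep a record of them in order to follow its own plan. Naming that record is study conduct, and it does not alter the analysis.

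**Conclusion.** The observation is accurate as a gap in wording, but it does not call for a change. The measure is a count of days over a wear period fixed at 8 weeks in both arms. An analyst would take days worn from the device or app record, state the rule used for a day worn, and report the count (out of 56 if a percentage is wanted) alongside the number and timing of withdrawals. A reader could then derive either percentage.

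Following the plan as written gives no wrong result. The gap of 2.5 to 22.5 points between the two denominators rests on assumed dropout of 10% to 30%, exit at day 14 to 42, perfect wear until exit, and conversion of the stated count to a percentage. It is not a bias in anything that the plan defines, and no difference between arms is implied. With no threshold, test or progression rule on adherence, and with Aim 2, sample size and power unaffected, writing the definitions down would be tidy but would change no conclusion.
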